10.3 Eliciting AEs

If the subject reports an AE, it is the Investigator's responsibility to acquire sufficient information in order to assess causality. This may require additional laboratory testing, physical examinations, telephone contacts, etc.

In order to avoid bias in eliciting AEs, subjects should be asked a non-leading question, such as "How are you feeling?" It is also important to question the subject in a non-leading way about changes in their health or concomitant medication usage since their last visit. This information should be collected prior to completion of assessments at all study visits. In addition, any symptoms/conditions reported during assessments and deemed to be clinically significant by the Investigator will be assessed as AEs.

10.4 Assessing AEs

10.4.1 Intensity/Severity

The medical assessment of intensity will be determined by using the following definitions:

Mild: The AE is easily tolerated and does not interfere with usual activity.

Moderate: The AE interferes with daily activity, but the subject is still able to function.

Severe: The AE is incapacitating, and the subject is unable to work or complete

usual activity.

Every change in intensity of a particular AE experienced by the subject during the course of the event is recorded.

It is important to note the distinctions between severe AEs and SAEs. Severity is a classification of intensity of a specific event (as in mild, moderate, or severe myocardial infarction); however, the event itself may be of relatively minor medical significance (such

as severe headache). An SAE, however, is an AE that meets any of the regulatory specified criteria required for designation as seriousness described in Section 10.7.1, i.e., a headache may be severe (interferes significantly with subject's usual function but would not be classified as serious unless it met 1 of the criteria for SAEs).

10.4.2 Causality and Reporting

An Investigator who is qualified in medicine must make the determination of relationship to investigational product for each AE and SAE. The Investigator should decide whether, in her/his medical judgement, there is a reasonable possibility that the event may have been caused by the investigational product.

If there is no valid reason for suggesting a relationship, then the AE/SAE should be classified as unrelated or unlikely related and an alternative suspected aetiology should be provided if available (i.e., concomitant medications, intercurrent illness/events). Otherwise, if there is any valid reason, even if undetermined or untested, for suspecting a cause-and-effect relationship between the investigational product and the occurrence of the AE/SAE, then the AE/SAE should be considered certainly, probably/likely, or possibly related.

The following additional guidance may be helpful:

Term	Relationship	Definition
Certain	Yes	Event or laboratory test abnormality, with plausible time relationship to drug intake
		Cannot be explained by disease or other drugs
		• Response to withdrawal plausible (pharmacologically, pathologically)
		• Event definitive pharmacologically or phenomenologically (i.e., an objective and specific medical disorder or a recognised pharmacological phenomenon)
		Rechallenge satisfactory, if necessary.
Probable/ Likely	Yes	• Event or laboratory test abnormality, with reasonable time relationship to drug intake
		• Unlikely to be attributed to disease or other drugs
		Response to withdrawal clinically reasonable
		Rechallenge not required.
Possible	Yes	• Event or laboratory test abnormality, with reasonable time relationship to drug intake
		Could also be explained by disease or other drugs
		• Information on drug withdrawal may be lacking or unclear.
Unlikely	No	• Event or laboratory test abnormality with a time to drug intake that makes a relationship improbable (but not impossible). Disease or other drugs provide plausible explanation.
Unrelated	No	 Event or laboratory test abnormality which is clearly related to circumstances not connected with the drug intake.

If the causal relationship between an AE/SAE and the investigational product is determined to be "certainly, probably/likely, or possibly related", the event will be considered to be

related to the investigational product for the purposes of expedited regulatory reporting. In circumstances where the causal relationship has not been provided, the event will be considered as related and qualify for expedited regulatory reporting.

10.4.3 Outcome Categorisation

Outcome may be classified as: recovered/resolved (i.e., without sequelae); recovered/resolved with sequelae; recovering/resolving; not recovered/not resolved; fatal; or unknown (if follow-up is not possible).

If the outcome of an SAE is reported as recovered/resolved with sequelae, the Investigator should specify the kind of sequelae on the SAE form. If the outcome of an SAE is reported as unknown, the Investigator should specify (on the SAE form) the rationale why unknown was selected.

"Fatal" should be recorded as an outcome when the AE results in death. If more than 1 AE is possibly related to the subject's death, the outcome of death should be indicated for the AE that, in the opinion of the Investigator, is the most plausible cause of death. All other ongoing AE/SAEs will be recorded as not recovered/not resolved at the time of death.

In case of a fatal outcome, the Investigator should provide a working diagnosis (event which caused outcome, e.g., death due to fatal myocardial infarction) instead of reporting only death; and an autopsy report should be provided where possible. If the cause of death later becomes available (e.g., after autopsy), this working diagnosis should be replaced by the established cause of death.

Although "fatal" is usually an outcome of an event, events such as sudden death or unexplained death should be reported as SAEs.

10.5 Recording and Reporting

10.5.1 Persistent or Recurrent AEs

AEs that extend continuously, without resolution, between trial assessments should only be recorded once in the eCRF.

The initial severity of the event should be recorded, and the severity should be updated to reflect the most extreme severity any time the event worsens.

AEs that resolve and subsequently recur should have each recurrence recorded separately in the eCRF.

All AEs persisting at the time of study completion will be followed by the Investigator through contact with the subject until resolution or stabilisation, or the subject is lost to follow-up and cannot be contacted. The outcome must be documented in the subject's source documents.

10.5.2 Diagnosis Versus Signs and Symptoms

Where possible, the Investigator should report a diagnosis rather than individual signs and symptoms or abnormal laboratory values. However, if a constellation of signs and/or symptoms cannot be medically characterised as a single diagnosis or syndrome at the time of reporting, each individual event should be recorded in the eCRF. If a diagnosis is subsequently established, all previously reported AEs based on signs and symptoms should be nullified and replaced by 1 AE report based on the single diagnosis, with a starting date that corresponds to the starting date of the first symptom of the eventual diagnosis.

The Investigator should use standard medical terminology/concepts; avoid colloquialisms and abbreviations. Only 1 AE term should be recorded in each event field in the eCRF.

10.5.3 Pre-existing Medical Conditions

A pre-existing medical condition is one that is present at the screening visit for this study. Such conditions should be recorded on the medical history eCRF. A pre-existing medical condition should be recorded as an AE only if the frequency, severity, or character of the condition worsens during the study. When recording such events on the AE eCRF, it is important to convey the concept that the pre-existing condition has changed by including applicable descriptors (e.g., "more frequent headaches").

10.5.4 Clinical Laboratory Evaluations

Not every out-of-range laboratory result qualifies as an AE. A laboratory investigation result must be reported as an AE if it meets any of the following criteria:

- Is accompanied by clinical symptoms
- Results in a change in study treatment (e.g., dosage modification, treatment interruption, or treatment discontinuation)
- Results in a medical intervention (e.g., potassium supplementation for hypokalaemia) or a change in concomitant therapy
- Presents shift of a parameter from a normal value to a pathological value, or results in a deterioration of common terminology criteria grade, or a further worsening of an already pathological value
- Is clinically significant in the Investigator's judgement

It is the Investigator's responsibility to review all laboratory findings. Medical and scientific judgement should be exercised in deciding whether an isolated laboratory abnormality should be classified as an AE. When evaluating such changes, the extent of deviation from the reference range, the duration until return to the reference range, either while continuing treatment or after the end of treatment with the investigational product,

and the range of variation of the respective parameter within its reference range, must be taken into consideration.

If, at the end of the treatment phase, there are pathological laboratory values which were not present at baseline, further clinical or laboratory investigations should be performed until the values return to within reference range or until a plausible explanation (e.g., concomitant disease) is found for the pathological laboratory values.

The Investigator should decide, based on the above criteria and the clinical condition of a subject, whether a change in a laboratory parameter is clinically significant and therefore represents an AE. If the Investigator considers such an AE as serious (e.g., medically significant event fulfilling criteria per Section 10.7.1), it must be reported as an SAE.

If a laboratory abnormality meeting the above criteria is a sign of a disease or syndrome only the diagnosis should be recorded in the eCRF.

If a laboratory abnormality meeting the above criteria is not a sign of a disease or syndrome, the abnormality itself should be recorded in the eCRF, along with a descriptor indicating if the test result is above or below the normal range (e.g., "elevated potassium," as opposed to "abnormal potassium").

If the laboratory abnormality can be characterised by a precise clinical term per standard definitions, the clinical term should be recorded as the AE, for example, hypercalcaemia or hypoglycaemia. Observations of the same laboratory abnormality from visit to visit should not be repeatedly recorded in the eCRF unless the aetiology changes. The initial severity of the event should be recorded, and the severity or seriousness should be updated any time the event worsens.

All pathological laboratory findings/values diagnosed throughout the treatment period should be reviewed by the Investigator to provide a final clinical assessment in view of the dynamic of laboratory changes/abnormalities.

10.5.5 Worsening of the Disease Under Study

Symptoms and signs of the disease under study should not be considered AEs as long as they are not regarded as worsening of the clinical features of the disease under study. If a sign or symptom of the disease has unexpectedly worsened in severity or frequency or changed in nature at any time during the study, the symptoms and signs should be recorded as AEs, and clearly marked as worsening of the signs or symptoms in the eCRF.

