1.2.2.2 Safety of IV Difelikefalin

In general, IV difelikefalin has been well tolerated in both single and repeat-dose clinical studies for up to 12 weeks at doses $<5 \mu g/kg$ in healthy volunteers and subjects with CKD.

In subjects with normal renal function, IV difelikefalin produces a transient and generally dose-related increase in urine output without loss of electrolytes (0 to 12 hours after dosing). This aquaretic effect (i.e., free water loss) is a known pharmacological effect of KOR agonists and is managed with fluid replacement, as applicable.

In healthy volunteers exposed to IV difelikefalin, the most common treatment-emergent adverse events (TEAEs) ($\geq 5.0\%$ of subjects) with an incidence $\geq 1.0\%$ greater compared with placebo were, in descending frequency, paraesthesia, hypoaesthesia, dizziness, sedation, headache, and fatigue. There was an apparent dose-response relationship with difelikefalin for the majority of TEAEs, with the highest incidence observed at IV difelikefalin doses $> 5~\mu g/kg$. There was 1 reported SAE of sinus tachycardia in a difelikefalin-treated subject and none in placebo-treated subjects. No specific TEAEs leading to investigational product discontinuation occurred in > 1 subject.

In subjects with CKD on HD exposed to IV difelikefalin, the most common TEAEs (≥5.0% of subjects) with an incidence ≥1.0% greater compared with placebo were, in descending frequency, diarrhoea, nausea, insomnia, fall, hypotension, abdominal pain, dizziness, vomiting, hyperkalaemia, headache, pneumonia, and dyspnoea. The most common SAEs (≥1.0% of subjects) among difelikefalin-treated subjects with an incidence ≥1.0% greater compared with placebo were, in descending frequency, pneumonia, fluid overload, sepsis, hyperkalaemia, respiratory failure, mental status changes, acute myocardial infarction, gastrointestinal haemorrhage, syncope, asthenia, and non-cardiac chest pain. Observed SAEs were consistent with underlying medical conditions in the subject population. The most common TEAEs leading to investigational product discontinuation among difelikefalin-treated subjects were cardiac arrest, somnolence, and dizziness.

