5.2 Inclusion Criteria

Subjects are eligible to be included in the study only if all of the following inclusion criteria apply:

- 1. Appropriate written informed consent has been provided by subject or legally acceptable representative. Written informed consent must be provided before any study-specific procedures are performed, including screening procedures.
- 2. Subjects have the ability to understand the requirements of the study, in the Investigator's opinion.
- 3. Chinese subjects aged ≥ 18 to 85 years (inclusive), at the time of consent.
- 4. End-stage renal disease (ESRD) subjects who have been on HD for at least 3 months before enrolment in the study and are currently on HD 3 times per week. Subjects with or without associated pruritus may be enrolled.
- 5. Subjects with a prescription dry body weight between 40 and 100 kg, inclusive.
- 6. If female, is not pregnant, or nursing.
- 7. If female:
 - a. Is surgically sterile; or
 - b. Has been amenorrhoeic for at least 1 year and is over the age of 55 years; or
 - c. Has a negative serum pregnancy test within 7 days before first dose of investigational product, and agrees to use adequate contraceptive precautions (e.g., hormonal contraceptives, barrier with spermicide, intrauterine device, vasectomised partner, or abstinence) from the time of informed consent until 7 days after the last dose of investigational product. Note: If the result from serum pregnancy testing at screening is indeterminate due to possible human chorionic gonadotropin elevation secondary to ESRD unrelated to pregnancy, a serum pregnancy re-test may be repeated prior to treatment Day 1 to establish if a negative result can be confirmed.

8. If male, agrees not to donate sperm from the first dose of investigational product administration (Day 1) until 7 days after last dosing, and agrees to use a condom with spermicide or abstain from heterosexual intercourse during the study until 7 days after the last dose of investigational product. Note: No restrictions are required for a vasectomised male, provided his vasectomy was performed ≥4 months prior to screening.

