12.10.1 Adverse Events

All AEs and pre-treatment AEs will be coded using MedDRA to MedDRA SOC and PT for standardisation and summary purposes.

All reported AEs will be included in summary tables and in by-subject AE listings.

An AE is defined as any AE that has an onset on or after the first investigational product administration, or any pre-existing condition that has worsened on or after the first administration of investigational product.

A pre-treatment AE is defined as any AE that has an onset before the first investigational product administration.

The number and percentage of subjects experiencing AEs, as well as the number of events will be summarised. A subject will be counted only once in the incidence count for a MedDRA SOC or PT, although a subject may have multiple occurrences (start and stop) of an event associated with a specific MedDRA SOC or PT.

In addition, the incidence and percentage of subjects experiencing treatment-emergent SAEs and AEs leading to investigational product discontinuation will be presented by the appropriate MedDRA SOC and PT.

AEs will also be summarised by severity and by relationship to investigational product. If the severity and/or relationship to the investigational product of an AE is missing, a worst-case scenario will be assumed (i.e., the AE will be categorised as "severe" and/or

"related" to the investigational product). If a subject reports the same AE multiple times the event with the worst severity and the strongest relationship to investigational product will be tabulated.

An overall summary table will be provided, presenting the number and percentage of subjects as well as the number of events for AEs, SAEs, treatment-emergent deaths, treatment-related AEs, treatment-related SAEs, severe AEs, AEs leading to investigational product discontinuation and AESIs.

In addition, the following summary tables will be presented and will include the number and percentage of subjects as well as the number of events for:

- AEs by SOC and PT
- SAEs by SOC and PT
- AEs by SOC, PT, and maximum severity
- Related AEs by SOC and PT
- AEs leading to investigational product discontinuation by SOC and PT
- AESIs by PT
- Related AESIs by PT

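### Section 10.5.5 ties recording of disease worsening to its being unexpected, at odds with its own first sentence and with 10.5.3, and leaves the disease under study undefined, so some non-serious worsening may go unrecorded

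*Combined protocol and SAP*

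**What the plan says.** Three parts of the protocol deal with worsening of something the subject already has.

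- **Section 10.5.5** (disease under study). The first sentence sets an exclusion: "Symptoms and signs of the disease under study should not be considered AEs as long as they are not regarded as worsening". The second gives the instruction to record, under the condition "If a sign or symptom of the disease has unexpectedly worsened in severity or frequency or changed in nature".
- **Section 10.5.3** (pre-existing conditions). Scope: "A pre-existing medical condition is one that is present at the screening visit for this study". Rule: such a condition "should be recorded as an AE only if the frequency, severity, or character of the condition worsens during the study".
- **Section 12.10.1** (what is tabulated). Besides events with onset after first dose, an AE includes "any pre-existing condition that has worsened on or after the first administration of investigational product".

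The phrase *disease under study* is used only in 10.5.5 and is not defined. On the population, Section 5.2 requires ESRD on haemodialysis and adds: "Subjects with or without associated pruritus may be enrolled". Section 3.4 makes AE incidence part of the secondary endpoint.

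**The concern.** Expectedness normally decides how quickly an event is reported, not whether it is written down. This protocol uses it that way in 10.6.2 and 10.7.3. In 10.5.5 it enters the recording threshold instead, and two sites could treat the same event differently. One, following 10.5.3, records a worsened symptom. Another, following the second sentence of 10.5.5, leaves it out as usual for a dialysis patient.

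The undefined disease widens the room for this. If it means CKD-associated pruritus, 10.5.5 touches only itch. If it means ESRD, a natural reading for a subject without pruritus, it can reach symptoms that also appear among the drug's common adverse effects in Section 7.1. Headache shows the clash: 10.5.3 uses headaches becoming more frequent as its example of a worsening to record, and headache is on the 7.1 list.

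An event never recorded gets no causality assessment under 10.4.2 and appears in no table or listing. For AEs that are recorded, 12.10.1 takes the worst case when severity or relationship is missing. Here the error would run the other way.

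**Working it through.** The plan states no figure on this point and the sample size rests on no formula, so the check is mainly a comparison of texts.

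**Step 1. The rules side by side**

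| Section | What it governs | Trigger | Expectedness test? |
|---|---|---|---|
| 10.5.5, first sentence | Exclusion of disease symptoms | Not regarded as worsening | No |
| 10.5.5, second sentence | Instruction to record | Worsened, or changed in nature | Yes |
| 10.5.3 | Recording of conditions present at screening | Worse in frequency, severity or character | No |
| 12.10.1 | Tabulation | Worsened on or after first dose | No |

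A disease symptom that worsens as expected leaves the exclusion in the first sentence but does not meet the instruction in the second. Section 10.5.5 alone does not say what to do with it. ESRD, and any pruritus already present, also fall within 10.5.3, which points to recording. Taken literally, 10.5.3 says when *not* to record, but it goes on to explain how to word such events, so its intent is clear. Section 12.10.1 agrees with 10.5.3, but it is an analysis definition. It cannot restore an event the site did not enter.

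**Step 2. What other sections capture, expected or not**

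- 10.5.4: a laboratory result that worsens from an already pathological value, comes with symptoms, or leads to intervention.
- 9.2 and 10.5.6: noteworthy vital sign changes, and vital sign or ECG abnormalities with symptoms, a diagnosis or an intervention.
- 9.1: a clinically relevant new or worsened condition behind a change in concomitant treatment.
- 10.7.1: any worsening that meets a seriousness criterion.
- 10.1: a new post-dose event that is not a sign or symptom of the disease.

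**Step 3. What is left**

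Removing these leaves non-serious worsening of an existing symptom, with no treatment change and no laboratory, vital sign or ECG trigger. If the disease is read as ESRD, five of the twelve effects listed in 7.1 could fall here: nausea, vomiting, dizziness, headache and dyspnoea. That classification is a judgement; the protocol lists no symptoms of the disease under study.

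**Step 4. Scale**

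Inputs: n = 30 (Section 12.2), assuming all 30 are dosed and in the safety set.

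- Loss in a term's incidence when k subjects have their only event of that term unrecorded: k/30.
- k = 1: 1/30 = 3.3 points. k = 2: 2/30 = 6.7 points. k = 3: 3/30 = 10.0 points.
- For comparison, a term with a true incidence of 5% (the cut-off for the 7.1 list, used here only as an illustration) is expected in 30 × 0.05 = 1.5 subjects, and is seen at least once with probability 1 − 0.95^30 = 78.5%. One missed subject can therefore matter for such a term.

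The value of k cannot be derived from the documents.

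**The case against.** The strongest reply is that this is loose drafting with little effect. Section 10.5.5 contains no *only*, and its first sentence implies that any worsening ceases to be excluded. Section 10.5.3 already covers ESRD. The routes in Step 2 catch most of what matters, and 10.3 has clinically significant symptoms raised during assessments treated as AEs. Dizziness is a named event of special interest in 10.8.4.1, so a site is unlikely to dismiss it.

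Much of this stands, and it rules out several stronger readings that a reader might infer:

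- *Worsening counts only if unexpected.* The section does not say so. It is ambiguous between two adjacent sentences.
- *Hyperkalaemia and hypotension are lost.* Most hyperkalaemia is caught by 10.5.4 and much hypotension by 9.2 and 10.5.6.
- *The remark in 1.2.2.2 that "Observed SAEs were consistent with underlying medical conditions in the subject population" shows events being discounted.* It concerns SAEs, which 10.7.1 captures whether or not they were expected.
- *The lack of a control arm is what makes the loss irrecoverable.* A control arm would not recover unrecorded events either.
- *A particular total shortfall in incidence.* The documents give no rate for such worsening, and a subject with another recorded AE would not change any-AE incidence.

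Some of the reply does not stand. Scheduled vital signs are taken before dialysis and dosing follows it, so after each dose the next scheduled reading is two or three days later (Days 3, 5 and 8 in Table 1). That makes 10.5.6 a weak safeguard for transient post-dose hypotension. Sections 10.5.4 and 10.5.6 also direct that only the diagnosis be recorded when an abnormality is a sign of a disease. If that disease is pre-existing ESRD, the question may return to 10.5.3 against 10.5.5. Finally, 10.8.4.2 treats events of special interest as AEs so classified, so a worsening not recorded as an AE can miss that route too.

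**Conclusion.** The point holds in a limited form. Section 10.5.5 is ambiguous within itself, its recording instruction conflicts with 10.5.3 and does not match the definition in 12.10.1, and the disease it refers to is not identified.

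The exposure is confined to the category left in Step 3. It matters beyond itch only if sites read the disease as ESRD and let the second sentence of 10.5.5 prevail over 10.5.3; the documents permit that reading but do not require it. Any resulting bias in AE incidence is downward. Its size is 3.3 percentage points of a term's incidence per affected subject at n=30, with the number of subjects unknown. The amendment is worth making because it is cheap and the omission cannot be repaired at analysis.

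**What to change.** In Section 10.5.5:

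1. Delete *unexpectedly* from the second sentence.
2. State which condition *disease under study* means. CKD-associated pruritus would be the narrower choice, but the documents do not settle this, since pruritus is not an entry requirement. The sponsor should decide.
3. Cross-refer to 10.5.3, so that any worsening in frequency, severity or character is recorded as an AE whether or not it was expected.

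No change to 12.10.1 is needed. The cost is one edited paragraph, a line in site training and a few more AE records.
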